2.2 Antibiotic treatment

2.2.1 Pre-period

During the pre-period each participating site will be required to initiate treatment for ABSSSI with “usual care,” defined as investigator’s choice of antibiotic therapy (e.g., vancomycin, linezolid, and daptomycin), to each study subject who meets all study selection criteria. It is expected that choice of usual care will be site or physician specific. Dosing of each antibiotic agent should follow recommended guidelines, demonstrated for antibiotic agents in, but not limited to, Table 1 below. All included subjects require Gram-positive antimicrobial coverage for a known or suspected infection caused by susceptible isolates of the following microorganisms: *Staphylococcus aureus* (including methicillin-susceptible and methicillin-resistant strains), *Streptococcus pyogenes*, *Streptococcus agalactiae*, *Streptococcus dysgalactiae*, *Streptococcus anginosus* group (including *S. anginosus*, *S. intermedius*, *S. constellatus*) and *Enterococcus faecalis* (vancomycin susceptible strains).

2.2.2 Post-period

During the post-period, all enrolled subjects will receive treatment for ABSSSI with dalbavancin at each participating site. Dalbavancin will be administered as a single IV dose of 1500 mg over 30 minutes (1125 mg over 30 minutes if CrCl <30 mL/min, for those not on regularly scheduled dialysis).¹² Dalbavancin will be provided to sites by study sponsor.

2.2.3 Rationale of dose/regimen of antibiotic treatment

Usual care antibiotic therapy and dalbavancin will each be administered per relevant guidelines/manufacturer instructions (dosing provided in Table 1). Duration of treatment

with usual care will be left to the physician's discretion, as recommendations for several agents include a range (e.g., 10–14 days for linezolid).²⁴

2.2.4 Rationale for choice of comparator

Usual care will comprise investigator's choice of care and may therefore vary from subject to subject. This was selected to allow for comparisons of the new critical pathway, which includes use of dalbavancin, with "real world" treatment.

2.3 Subject identification

Patients presenting to the ED with an ABSSSI infection during both the pre- and post-periods will be assessed for inclusion and exclusion criteria. These criteria will be prepared as an annotated checklist for the study coordinator and/or study nurses to implement and document using a CRF. Information obtained through the annotated checklist coupled with physician assessment will define guideline-based patient identification criteria.

2.3.1 Pre-period

During the pre-period, the study coordinator and/or other study nurses will identify patients who may be eligible for the study. All hospital staff may be reminded (through posters or memorandums) to inform the study coordinator and/or other study nurses as soon as an ABSSSI patient is seen in the ED. The study coordinator will implement inclusion and exclusion criteria for the new critical pathway by patient interview and/or chart review. Inclusion criteria includes measurement of lesion size through a physician assessment (Appendix A), and clinical judgment that patient requires coverage for a known or suspected Gram-positive infection. Patients who meet all inclusion criteria and none of the exclusion criteria based on study coordinator assessment will be enrolled in the study or flagged for further review by core study team physicians, who will make the final enrollment decision. The treating physician will be blinded to protocol content and study enrollment decision. Study coordinator will then complete all additional elements of enrollment, including informed consent, and scheduling of follow-up.

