2.1 Overview

This study will employ a “pre-post” pragmatic design, which will consist of both a pre-period, or an observational baseline period, and a post-period, or an interventional period (Figure 1). During the pre-period, each participating site will implement the first component of the critical pathway through implementation of guideline-based criteria to identify patients at the point of care in the ED, obtain informed consent, and monitor enrolled subjects. Sites will initiate treatment for ABSSSI with “usual care,” defined as site- or physician-specific antibiotic treatment of ABSSSI with coverage for a known or suspected Gram-positive infection (e.g., vancomycin, linezolid, and daptomycin) to each study subject who meets all inclusion and exclusion criteria. Blinding of treating physician to subject enrollment in the study during the pre-period will ensure unbiased provision of usual care. During the “post” period, for all subjects who provide informed consent and are subsequently enrolled, each participating site will additionally implement the second component of the new critical pathway, use of dalbavancin, at the point of care in the ED to each study subject who meets all inclusion and exclusion criteria.

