As the study is pragmatic in nature, selection criteria will be minimal and designed to maximize the selection of “real-world” patients who are ideal candidates for treatment in the outpatient healthcare setting, but who are currently admitted to the hospital to receive treatment for ABSSSI. Site training is necessary for both adherence to the protocol and implementation of the new critical pathway, described in greater detail in Section 7, Study sites and administrative structure. Briefly, the core study team in conjunction with members of the contract research organization (CRO) will provide training to other members of the site study team, including all participating site physicians and other healthcare providers (i.e. nurses, pharmacists, and other staff) on protocol adherence and implementation of the new critical pathway. Protocol training will occur before enrolling subjects in both the pre- and the post-period. Before enrolling subjects in the post-period, training on implementation of the new critical pathway will occur over a two- to four-week period after the date of the last enrolled subject in the pre-period. In addition, ongoing reminders and orientations will be scheduled for sites as needed during both the pre- and post-period.

For both periods of interest, subject follow-up will begin on the day of study enrollment and end 44 days subsequently. This will reflect the 10 to 14-day period during which antibiotics are anticipated to be required for care of ABSSSI plus an additional 30 days to ascertain outcomes, such as health resource utilization.

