2.3.2 Post-period

During the post-period, the study coordinator and/or other study nurses will identify patients who may be eligible for the study. As in the pre-period, physicians or other appropriate healthcare providers may also identify subjects who are eligible for the study. All hospital staff may be reminded (through posters or memorandums) to inform the study coordinator and/or other study nurses as soon as an ABSSSI subject is seen in the ED. The study coordinator or treating physician will implement the checklist and enroll subjects into the study. Study coordinator will then complete enrollment, including informed consent, and scheduling of follow-up.

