3.0 Study Design

This study will employ a "pre-post" pragmatic design, which will consist of both a pre-period, or an observational baseline period, and a post-period, or an interventional period. The pre-period and post-period will consist of independent groups of patients. During the pre-period, each participating site will implement the first component of the critical pathway through implementation of guideline-based criteria to identify patients at the point of care in the ED, obtain informed consent, and monitor enrolled patients. Sites will initiate treatment for ABSSSI with "usual care," defined as site- or physician-specific antibiotic treatment of ABSSSI with coverage for a known or suspected Gram-positive infection (e.g., vancomycin, linezolid, and daptomycin) to each study patient who meets all inclusion and exclusion criteria. Blinding of treating physician to patient enrollment in the study during the pre-period will ensure unbiased provision of usual care. During the post-period, for all patients who provide informed consent and are subsequently enrolled, each participating site will additionally implement the second component of the new critical pathway, use of dalbavancin, at the point of care in the ED to each study patient who meets all inclusion and exclusion criteria. Sites are expected to transition to the post-period at the enrollment of 50 patients. There is no expectation for all sites to transition to the post-period at the same time.

For both periods of interest, patient follow-up spans the period beginning on the day of study enrollment and ends 44 days thereafter, which incorporates an initial care period of 14 days (reflecting the 10–14-day period during which most antibiotics are anticipated to be required for care of ABSSSI) and a subsequent “follow-up” period of 30 days. Study measures will be collected as described in the protocol and will be based on medical records, unless otherwise indicated.

A schedule of assessments is provided in Appendix A. Follow-up visits will be scheduled for approximately 24 hours after enrollment (post-period only), 48–72 hours after enrollment (post-period only), 14 days after enrollment (both periods), and 44 days after enrollment (both periods). Any additional visits to the visit schedule below will be at the discretion of the patient and treating physician.

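### The protocol relies on a pre-period blind of the treating physician that its own training, identification and usual-care rules do not secure

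*Protocol*

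**What the plan says.** Protocol 2.3.1 sets the blind for the pre-period: "The treating physician will be blinded to protocol content and study enrollment decision". Protocol 2.1 gives its purpose: "Blinding of treating physician to subject enrollment in the study during the pre-period will ensure unbiased provision of usual care". SAP 3.0 repeats this almost word for word. The scope differs between these places: 2.3.1 covers protocol content and enrolment, while Protocol 2.1 and SAP 3.0 mention enrolment only.

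Four other provisions bear on the blind.

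- **Training.** Protocol 2.1 has the core study team and the CRO train the rest of the site study team, "including all participating site physicians and other healthcare providers (i.e. nurses, pharmacists, and other staff) on protocol adherence". On timing it says: "Protocol training will occur before enrolling subjects in both the pre- and the post-period". Protocol 6.1 repeats the timing, and 6.2 places physicians on the site study team and makes that team answerable for following the protocol in both periods.
- **Pathway training.** This is separate and later. Protocol 2.1 says that "training on implementation of the new critical pathway will occur over a two- to four-week period after the date of the last enrolled subject" of the pre-period.
- **Identification.** Protocol 2.3.2, on the post-period, says: "As in the pre-period, physicians or other appropriate healthcare providers may also identify subjects who are eligible for the study".
- **Choice of usual care.** Protocol 2.2.4 says: "Usual care will comprise investigator's choice of care and may therefore vary from subject to subject". The synopsis and 2.2.1 also name the investigator. Protocol 2.1 and 2.2.1 add that the choice may be specific to the site or physician, and 2.2.3 leaves treatment duration to the physician.

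**The concern.** The trial has no concurrent control. The pre-period admission rate is the whole comparator, and the primary outcome is a physician's decision to admit. The plan recognises that knowledge of the study could change that decision, which is why it blinds the treating physician and presents the blind as what makes usual care unbiased.

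If the physician deciding on a pre-period patient has been trained on the protocol, or is the person spotting eligible patients, or is the investigator, that protection is gone. A physician who knows that the study concerns avoidable admissions might admit fewer patients, shrinking the apparent effect, or might shift practice the other way and inflate it. The final report would still describe the physicians as blinded.

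The planned analyses would not reveal this. The adjusted model in SAP 6.2.6.1 uses patient characteristics. The site admission counts in SAP 4.1 and 6.2.2 compare the two periods and give some view of background trends, but neither they nor any data item listed in the readable text records whether the deciding physician was trained or aware.

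**Working it through.** **Step 1. Set the rules side by side.**

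| Question | Rule supporting the blind | Rule working against it |
|---|---|---|
| Does the pre-period treating physician know the protocol? | No (Protocol 2.3.1) | Participating site physicians are trained on the protocol before the pre-period (2.1, 6.1); site-team physicians must follow it in both periods (6.2) |
| Who identifies eligible pre-period subjects? | Coordinator and study nurses (2.3.1) | Physicians also could, according to the back-reference in 2.3.2 |
| Who chooses usual care? | Choice specific to the site or physician (2.1, 2.2.1); duration at the physician's discretion (2.2.3) | The investigator (synopsis, 2.2.1, 2.2.4), who must know the protocol |

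The blind survives only if the treating physician is outside the site study team, does not identify subjects, and is not the investigator. No readable passage states any of these three conditions.

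**Step 2. Reproduce the plan's own figure.** Inputs from Protocol 5.3 and SAP 6.1.2: 38% against 23%, one-sided 0.05, 161 per period. With the normal approximation and pooled variance under the null,

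power = Φ( [d − 1.645·√(2·p̄(1−p̄)/n)] / √([p1(1−p1) + p2(1−p2)]/n) ).

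Here d = 0.15 and p̄ = 0.305. The null standard error is √(0.42395/161) = 0.0513, and the alternative one is √(0.4127/161) = 0.0506. Then (0.15 − 1.645 × 0.0513)/0.0506 ≈ 1.30, so power is 90.2%. With 10% attrition (161 × 0.9 ≈ 145) it is 87.4%. Since 80% power needs 116 per period, the stated minimum of 80% holds up to attrition of 1 − 116/161 = 28%. The sample-size statement is not in dispute.

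**Step 3. Show what the blind protects.** The documents give no size or direction for any effect of awareness, so the shifts below are assumptions. Each uses 161 per period and the formula above.

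| Assumed shift in pre-period rate | Apparent difference from 23% if lowered / raised | Power against 23% if lowered | Chance of a significant result if raised, with no true effect (38% post) |
|---|---|---|---|
| 0 points | 15 | 90% | 5% |
| 2 points | 13 / 17 | 82% | 10% |
| 5 points | 10 / 20 | 64% | 23% |
| 8 points | 7 / 23 | 41% | 42% |

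For the 5-point row: lowered, 38 − 5 − 23 = 10; raised, 38 + 5 − 23 = 20. The table shows sensitivity only; it does not estimate a bias.

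**The case against.** The strongest reply is that the text can be read consistently. Training in Protocol 2.1 goes to members of the site study team, and 2.3.1 distinguishes the treating physician from the core-team physicians who settle enrolment. An ED physician outside the team could therefore be untrained and unaware. Naming the investigator as chooser may be loose wording for the physician, as the neighbouring phrases suggest, and it refers to the antibiotic; no passage gives the admission decision to the investigator. The sentence in 2.3.2 is a single back-reference, and 2.3.1 itself gives identification to the coordinator and nurses. Above all, pathway training is held back until pre-period enrolment has ended.

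Much of this stands. A reader might infer that the blind cannot hold at any site. The documents do not support that, because a site that kept its treating physicians off the study team could preserve it. A reader might also count the posters or memoranda to staff, and the physician's lesion measurement in 2.3.1, as breaches. They are not breaches in themselves: a reminder to call the coordinator need not reveal the criteria or who was enrolled, and the text does not say that the treating physician takes the measurement.

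What does not stand is the inference that the blind is therefore secured. The favourable reading depends on an exclusion that the protocol never makes, and delaying pathway training does not meet the promise in 2.3.1 to withhold protocol content. Two sites could both follow this text, one with blinded physicians and one without.

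**Conclusion.** The concern holds in this form: the pre-period blind is not secured by the protocol's own rules, and the assurance in Protocol 2.1 and SAP 3.0 ("Blinding of treating physician to patient enrollment in the study during the pre-period will ensure unbiased provision of usual care") is stronger than those rules support. The conflict rests on the text alone.

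Whether the blind failed in practice is unknown. Any resulting bias could run in either direction, and its size cannot be derived from the documents. The figures above depend on assumed shifts and on the planning rates of 38% and 23%; they show only that shifts of a few points would matter to the primary test. The conclusion also assumes that no redacted passage or separate training document exempts treating physicians.

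**What to change.** Reconcile the synopsis, Protocol 2.1, 2.2.1, 2.2.4, 2.3.1, 2.3.2, 6.1 and 6.2, and SAP 3.0, as follows.

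1. Limit pre-period protocol training to coordinators, study nurses and core-team physicians. Train treating ED physicians only in the existing two- to four-week window before the post-period.
2. State that pre-period usual care and disposition are decided by a treating physician who is not a study investigator. In 2.3.2, delete the back-reference to the pre-period, or limit it to telling the coordinator about any ABSSSI patient.
3. For every pre-period patient, including those already enrolled, have study staff record from delegation and training logs whether the treating physician was study-trained. Do not ask the physician, since the question could itself unblind. Report the proportion trained and the admission rate by this status descriptively. Add an analysis excluding patients of trained physicians only if numbers allow; if most were trained, few patients would remain.
4. In Protocol 2.1 and SAP 3.0, state the blind as an aim and its possible failure as a limitation.

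Items 1 and 2 cannot reach patients already enrolled: the interim analysis took place at about 75 pre-period patients, and Protocol Version 3.0 already reflects its result. For them only items 3 and 4 apply, and logs show training, not awareness of a particular enrolment. The cost is wording changes, one log lookup per pre-period patient, one descriptive table, and perhaps slightly slower pre-period recruitment.

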2.3.3 Subject follow-up

Within both the pre- and post-periods, follow-up for each subject will begin on the day of enrollment (which is anticipated to be the date of treatment initiation) and conclude 44 days thereafter. Follow-up will therefore include the presumed "episode" of antibiotic therapy for ABSSSI (up to 14 days) and subsequent 30-day period.

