5.3 Sample size and sample size considerations

Hospital admission rate, which is correlated to total hospital time for the study population, was largely unknown for purposes of sample size estimation. The final enrollment to support hypothesis testing for a primary outcome of total admitted hospital days was initially calculated as 322 subjects (161 subjects in each period). The sample size was evaluated after a planned interim analysis of pre-period data once 75 subjects were enrolled in the pre-period. Based on results of the interim analysis, an adjustment was made at the time of the analysis to revise the primary outcome from total admitted hospital days to hospital admission rate at initial episode of care. The initially estimated final enrollment of 322 subjects, including adjustments for attrition, would support one-sided hypothesis testing (two-sample Pearson chi-square test for proportion difference with equal group weights using a normal approximation) with a significance level of 0.05 and at least 80% power assuming hospital admission rate comparing the pre- and post-periods were 38% versus 23%.

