5.0 Changes in the Protocol Specified Analyses

Infection characteristics described in the protocol including hyperglycemia (>120mg/dL blood glucose or site-specific definition), thrombocytopenia (<150,000 platelet count or site-specific definition), acidosis (<7.35 pH of the blood or site-specific definition or described in medical chart), hyponatremia (<135 mEq/L blood sodium or site-specific definition), uremia (as described in medical chart), and anemia (14-18 g/dL hemoglobin for men or 12-16 g/dL hemoglobin for women or site-specific definition) will not be derived from laboratory values or reported in analysis.

An interim analysis was performed after the enrollment of approximately 75 patients to evaluate the original sample size. It was determined a sample size greater than 322 would be needed for hypothesis testing of the primary outcome of total number of days spent in the hospital. Factors that contributed to the large sample size include:

- The observed variation was larger than the original estimate (SD = 3.0 days).
- The observed attrition rate was larger than the original assumption (10%).

Additionally, the observed mean total LOS was much smaller than the protocol assumption (4.0 days). It was determined that observing a statistically significant reduction in the total number of days spent in the hospital in the post-period was unlikely.

Based on results of the interim analysis, an adjustment was made at the time of the analysis to revise the primary outcome from total admitted hospital days to hospital admission rate at initial episode of care. The initially estimated final enrollment of 322 subjects, including adjustments for attrition, would support one-sided hypothesis testing (two-sample Pearson chi-square test for proportion difference with equal group weights using a normal approximation) with a significance level of 0.05 and at least 80% power assuming hospital admission rate comparing the pre- and post-periods were 38% versus 23%. This change has been reflected in the protocol, Amendment Version 3.0.

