Appendix B: Derived Variables

Analysis Section (Visit)	Variable (Units)	Definition
General (Baseline)	Enrollment date	Informed consent date
General (Baseline)	Baseline date	Initial ED admission date
General (Initial Care)	Initial care indicator	If enrollment date \leq date \leq enrollment date + 13 days then = Yes Else = No
General (Follow-up)	Follow-up indicator	If enrollment date + 14 \leq date \leq enrollment date + 43 days then = Yes Else = No
Demographics (Baseline)	Age (years)	Round down to nearest integer((Initial ED admission date - date of birth + 1)/365.25), when both dates are available.
Demographics (Baseline)	BMI	weight (kg)/ [height(m)] ² Where necessary, height and weight will be converted to proper units.
Infection Characteristics (Baseline)	CCI	Will be scored as described in Appendix C. Includes variables for raw score and 10 year survival probability.
Infection Characteristics (Baseline)	Fever	If temperature > 38 ° C then =Yes Else =No
Infection Characteristics (Baseline)	Morbid Obesity	If baseline BMI \geq 40 then =Yes Else =No
Infection Characteristics (Baseline)	SIRS Criteria Met	SIRS criteria include abnormalities in temperature, heart rate, respiration, and white blood cell count. Specifically included are: 
 Fever of more than > 38.0°C or hypothermia with temperature < 36.0°C

[figure not shown]
[figure not shown]
Analysis Section (Visit)	Variable (Units)	Definition
		
 • Tachycardia with heart rate > 90 beats/minute or • Tachypnea with respiratory rate of > 20 breaths/minute or PaCO₂ of less than 32mmHg • Abnormal white blood cell count: leukocytosis >12,000/microliter, leucopenia <4,000/microliter, or >10% immature cells (bands).^{3,4} 
If 2 or more criteria present = Yes Else = No

Antibiotic Medications (Initial Care and Follow-up)	Days Received Antibiotic Medication	
Σ (Medication end date – Medication start date +1), when both dates are available. If dates overlap (e.g., end date and next start date are identical) then subtract 1 from summation for each occurrence.

Primary Outcome	Hospital Admission At Initial Episode of Care	
If discharge destination from the initial episode of care = Hospital and the reported hospitalization where discharge date = hospital date is infection-related then = Yes, Else = No

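### No visible rule places pre-period consent before the ED disposition that defines the primary outcome, so admitted patients could be over-represented in that period

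*Protocol*

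**What the plan says.** **Outcome.** SAP Appendix B counts a patient as admitted if the discharge destination from the initial episode is the hospital and the matching stay is infection-related. The outcome is thus known once the index ED visit ends.

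**Pre-period.** Under Protocol 2.3.1 the coordinator screens by interview, chart review or both. The patient is then enrolled, or is flagged for core-team physicians to decide. The treating physician is blinded to that decision. Then: "Study coordinator will then complete all additional elements of enrollment, including informed consent, and scheduling of follow-up". Under SAP 6.1.1, at least one dose of any antibiotic qualifies the patient for the full analysis set (FAS).

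**Post-period.** Protocol 2.1 has dalbavancin used at the point of care in the ED "for all subjects who provide informed consent and are subsequently enrolled". Protocol 2.3.2 lets the coordinator or the treating physician enrol. The FAS requires a dalbavancin dose.

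**Timing in both periods.** Protocol 2.3.3 starts follow-up on the enrolment day, "which is anticipated to be the date of treatment initiation". SAP Appendix B defines the enrolment date as "Informed consent date" and the baseline date as the initial ED admission date. Protocol 7.3 requires consent before study-specific activities.

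**The concern.** A pre-post comparison of admission rates is fair only if entry to each cohort does not depend on disposition. An admitted patient can still be approached hours later, whereas a patient sent home has left. If consent may follow disposition in one period but hardly in the other, the outcome itself influences who is counted in one period only. The pre-period admission rate would then be too high, and a reduction would appear even if the pathway had no effect. The bias favours the pathway.

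Nothing planned would remove or reveal it. The logistic model in SAP 6.2.6.1 adjusts for baseline characteristics, which cannot undo selection on the outcome. The site admission counts (Protocol 2.1.2, SAP 6.2.2) address time trends, not who consented. SAP 6.2.1 keeps screen failures out of tables and listings and promises only approximate numbers and common reasons in the report text.

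**Working it through.** **Step 1: what ties consent to disposition in each period.**

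| Element | Pre-period | Post-period |
|---|---|---|
| Treating physician | Blinded to enrolment, so care need not wait for it | May enrol the patient |
| Before consent | Interview and/or chart review, possibly further physician review | Checklist |
| Treatment requiring prior consent | None (usual care) | Dalbavancin in the ED |
| Dose needed for the FAS | Any antibiotic | Dalbavancin |
| Visible rule: consent before disposition | None | None |

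The last row is the same for both periods. The asymmetry comes from the rows above it: a post-period patient approached only after leaving the ED would have missed the dose in the ED that the pathway calls for. A pre-period patient approached at that stage still qualifies.

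**Step 2: the plan's own figure.** Protocol 5.3 specifies "one-sided hypothesis testing (two-sample Pearson chi-square test for proportion difference with equal group weights using a normal approximation) with a significance level of 0.05", at least 80% power, admission rates of 38% versus 23%, and 161 subjects per period. With pooled variance under the null and no continuity correction:

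- Mean rate (0.38 + 0.23)/2 = 0.305.
- SE under the null = √(2 × 0.305 × 0.695/161) = 0.0513.
- SE under the alternative = √((0.38 × 0.62 + 0.23 × 0.77)/161) = 0.0506.
- Power = Φ((0.15 − 1.645 × 0.0513)/0.0506) = Φ(1.296) = 90.2%.

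With 10% attrition (145 per period) power is 87.4%. Eighty per cent needs 116 per period, which allows about 28% attrition (1 − 116/161). The stated power reproduces, so the sample size is not at issue.

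**Step 3: illustration of selection.** Let p be the true admission rate, equal in both periods. Let r be the enrolment probability of released patients divided by that of admitted patients in the pre-period, with r = 1 in the post-period. The apparent pre-period rate is

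q = p / (p + (1 − p) × r).

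The values of r, the post-period value of 1 and p = 30% are all assumptions; none is in the documents. With p = 0.30:

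- r = 0.9: q = 0.30/0.93 = 32.3%
- r = 0.8: q = 0.30/0.86 = 34.9%
- r = 0.7: q = 0.30/0.79 = 38.0%

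Putting q and p into the Step 2 formula with 161 per period gives the probability of rejecting when there is no pathway effect:

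| r | p = 23% | p = 30% | p = 38% |
|---|---|---|---|
| 1.0 | 5% | 5% | 5% |
| 0.9 | 11% | 11% | 12% |
| 0.8 | 22% | 24% | 25% |
| 0.7 | 41% | 45% | 47% |

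The outer columns use the plan's two rates as the common true rate. The result depends little on p and strongly on r.

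**The case against.** The strongest reply is that the described flow already points to early consent. Protocol 2.1 puts pre-period identification at the point of care in the ED, with consent next in the list. Protocol 2.3.1 allows reminders asking staff to report patients as soon as they are seen. Protocol 2.3.3 expects enrolment on the day treatment starts, in both periods. This stands as evidence of intent and makes heavy selection less likely, but none of it sets a deadline for consent. Protocol 7.3 does not set one either, because usual care and the admission decision are not described as study-specific activities.

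Four stronger readings are tempting and are not supported:

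- *The consent sentence in 2.3.1 shows the asymmetry by itself.* Protocol 2.3.2 has nearly the same sentence for the post-period.
- *Post-period disposition is fixed to come after consent.* Only the order consent, then dalbavancin in the ED, is stated. Nothing visible puts dosing before the disposition decision, and SAP 6.2.9 tabulates reasons why post-period patients were not discharged to outpatient care the same day.
- *Separate enrolment and baseline dates in Appendix B show that consent can follow disposition.* Those definitions apply to both periods, and the dates differ whenever an ED stay crosses midnight before consent.
- *First-dose adverse events can be lost only in the pre-period.* Recording starts at consent in both periods, and no visible text bars an antibiotic dose before consent in the post-period.

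The schedule tables and the design figure are not visible, so the absence of a rule can be asserted only for the text that can be read.

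**Conclusion.** The point holds as a gap in the design that allows one-directional bias in the primary comparison. It is not evidence that bias occurred. It rests on the dalbavancin requirement, which limits late consent in the post-period only, and on the lack of any comparable anchor in the pre-period.

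The size cannot be derived from the documents. Under the stated assumptions, a 10% shortfall in enrolling released patients (r = 0.9) roughly doubles the 5% error rate, and a 30% shortfall raises it to between 41% and 47% across the three true rates shown. If selection also operated in the post-period, the net bias would differ. With consent timed alike relative to disposition in both periods, this bias disappears and the sample size is unaffected.

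**What to change.** 1. **Protocol 2.3.1 and 2.3.2, for any remaining enrolment.** State that consent must be signed before the disposition decision (admission or observation order, or release), and record both times. This cannot repair pre-period patients already enrolled, so items 2 and 3 are needed for them.
2. **SAP 6.2.6.1.** Tabulate by period the consent date, with the time where source documents hold it, relative to the admission or observation order where available and otherwise to ED release. The two reference points differ, since a patient may consent after the decision while still in the ED. Show same-day cases of unknown order as a separate category. Repeat the primary and adjusted analyses excluding consents after disposition, first with the same-day unknown cases included and then with them excluded.
3. **Enrolment logs.** Tabulate eligible but unenrolled patients by disposition and period, where recorded. This is the most direct check on selective enrolment.

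The cost is a protocol sentence, a derived variable, two tables and one set of sensitivity analyses. The drawbacks are fewer patients in the sensitivity analyses and incomplete timing for patients already enrolled.
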